# 6.1.2 Serious Adverse Events

The terms "severe" and "serious" are not synonymous. Severity (or intensity) refers to the grade of an AE (see below). "Serious" is a regulatory definition and is based on subject or event outcome or action criteria usually associated with events that pose a threat to a subject's life or functioning. Seriousness (not severity) serves as the guide for defining regulatory reporting obligations from the sponsor to applicable regulatory authorities.

An AE should be classified as an SAE if it meets any one of the following criteria:

- It results in death (i.e., the AE actually causes or leads to death).
- It is life-threatening (i.e., the AE, in the view of the investigator, places the subject at immediate risk of death. It does not include an AE that, had it occurred in a more severe form, might have caused death).
- It requires or prolongs in-patient hospitalization.

- It results in persistent or significant disability/incapacity (i.e., the AE results in substantial disruption of the subject's ability to conduct normal life functions).
- It results in a congenital anomaly/birth defect in a neonate/infant born to a mother exposed to the investigational product.
- It is considered a significant medical event by the investigator based on medical judgment (e.g., may jeopardize the subject or may require medical/surgical intervention to prevent one of the outcomes listed above).

# 6.1.3 Severity

Definitions found in the CTCAE version 4.03 or higher will be used for grading the severity (intensity) of nonhematologic and hematologic AEs. The CTCAE v4.03 displays Grades 1 through 5 with unique clinical descriptions of severity for each referenced AE. Should a subject experience any AE not listed in the CTCAE, the following grading system should be used to assess severity:

- Grade 1 (Mild AE) experiences which are usually transient, requiring no special treatment, and not interfering with the subject's daily activities
- Grade 2 (Moderate AE) experiences which introduce some level of inconvenience or concern to the subject, and which may interfere with daily activities, but are usually ameliorated by simple therapeutic measures
- Grade 3 (Severe AE) experiences which are unacceptable or intolerable, significantly interrupt the subject's usual daily activity, and require systemic drug therapy or other treatment
- Grade 4 (Life-threatening or disabling AE) experiences which cause the subject to be in imminent danger of death
- Grade 5 (Death related to AE) experiences which result in subject death.

# 6.2 DOCUMENTING AND REPORTING OF ADVERSE AND SERIOUS ADVERSE EVENTS

The investigator is responsible for ensuring that all AEs and SAEs that are observed or reported during the study, as outlined in the prior sections, are recorded on the CRF. All SAEs must be reported on the SAE form or clinical database.

# 6.2.1 Adverse Event Reporting Period

After the signing of the ICF and prior to the first dose of study drug, all SAEs must be reported. After the first dose of study drug, all AEs/SAEs, irrespective of attribution of causality, must be reported.

For acalabrutinib, all AEs will be reported until 30 days after the last dose of acalabrutinib or the start of new anticancer therapy (whichever comes first). After this period, investigators should report SAEs or other AEs of concern that are believed to be related to prior treatment with acalabrutinib.

For pembrolizumab, all AEs must be reported through 30 days after the last dose of pembrolizumab; any SAEs, or follow-up to an SAE, including death due to any cause other than progression of the cancer under study, must be reported through 90 days after the last dose or 30 days after the last dose of pembrolizumab if the subject initiates a new anticancer therapy within the 90-day posttreatment timeframe.

SAEs considered related to study drug(s) or study procedures occurring after the end of the AE reporting period (as defined above) must be reported.

All AEs and SAEs that occur during the reporting period should be followed to resolution or until the investigator assesses the subject as stable, the subject is lost to follow-up or withdraws consent. Resolution/stable means the subject has returned to baseline state of health or the investigator does not expect any further improvement or worsening of the event.

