# 4.3 SAFETY FOLLOW-UP VISIT

Each subject should be followed for 30 days (+7) after his or her last dose of study drug (i.e., the "safety follow-up visit") to monitor for resolution or progression of AEs (see Section 6.2.7) and to document the occurrence of any new events, regardless of whether the subject receives a new anticancer therapy or demonstrates disease progression within this timeframe; after this period, investigators should report SAEs or other AEs of concern that are believed to be related to prior treatment with acalabrutinib (see Section 6.2.1). Subjects who withdraw consent for study treatment should still be encouraged to complete the safety follow-up assessments, but these assessments cannot be mandated if subject consent for further study participation is withdrawn. The Schedules of Assessments (Appendix 5 and Appendix 6) describe the procedures required for safety follow-up.

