# 6.2.2 Assessment of Adverse Events

Investigators will assess the occurrence of AEs and SAEs at all subject evaluation timepoints during the study. All AEs and SAEs whether volunteered by the subject, discovered by study personnel during questioning, or detected through physical examination, or other means, that occur to any subject from the time of first dose through 30 days following the cessation of study drug(s), and all SAEs that occur to any subject receiving pembrolizumab from the time of first dose through 90 days following cessation of pembrolizumab, or 30 days following cessation of pembrolizumab if the subject initiates new anticancer therapy (whichever is earlier) will be recorded in the subject's medical record and on the AE CRF.

Disease progression itself is not considered an AE unless it is considered to be drug-related by the investigator; however, signs and symptoms of disease progression may be recorded as AEs or SAEs.

Each recorded AE or SAE will be described by its diagnostic term, duration (e.g., start and end dates), severity, regulatory seriousness criteria, if applicable, suspected relationship to the study drugs (see following guidance), and any actions taken. The causality of AEs to the study drugs will be assessed by means of the question: 'Is there a reasonable possibility that the event may have been caused by the study drugs?' per FDA guidance on safety reporting requirements (FDA Drug Safety Communication 2012).

See Appendix 3 for more detail on assessing causality.

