9.7.1 Adverse Events

The Medical Dictionary for Regulatory Activities (MedDRA) will be used to code all AEs to a system organ class and a preferred term. The severity of the AE will be assessed by National Cancer Institute (NCI) Common Terminology Criteria for Adverse Events (CTCAE) Version 4.03 or higher. Drug-related AEs are those assessed by investigator as related.

Treatment-emergent AEs are defined as those events that occur (actual or imputed start date) on or after the first dose of study drug, through the treatment phase, and within 30 days following the last dose of study drug.

Treatment-emergent AEs will be summarized by system organ class and preferred terms in descending order of frequency, by NCI toxicity grade and by relationship to study drug. The same summary will be provided for serious treatment-emergent AEs and drug-related serious treatment-emergent AEs, treatment-emergent AEs leading to treatment discontinuation, dose reductions and dose withheld.

Death information is reported in the study exit CRF for all deaths. Incidences of deaths are to be reported, along with the primary cause of death.

AE by subject listing and death listing will be provided.

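### Protocol 6.2.1 can end routine AE reporting for acalabrutinib at new anticancer therapy, while Protocol 4.3, 6.2.2 and the SAP's TEAE window run a fixed 30 days

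*Protocol*

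**What the plan says.** Four places define when post-treatment AE collection or counting ends.

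- **Protocol 6.2.1, acalabrutinib:** "all AEs will be reported until 30 days after the last dose of acalabrutinib or the start of new anticancer therapy (whichever comes first"). Reporting then narrows: "After this period, investigators should report SAEs or other AEs of concern that are believed to be related to prior treatment with acalabrutinib".
- **Protocol 6.2.1, pembrolizumab:** "all AEs must be reported through 30 days after the last dose of pembrolizumab". New therapy does not shorten this AE period; it shortens only the 90-day SAE period.
- **Protocol 4.3:** "Each subject should be followed for 30 days (+7) after his or her last dose of study drug". New events in that time are to be documented "regardless of whether the subject receives a new anticancer therapy or demonstrates disease progression within this timeframe". For what follows the period, 4.3 refers the reader to 6.2.1.
- **Protocol 6.2.2:** all AEs and SAEs "that occur to any subject from the time of first dose through 30 days following the cessation of study drug(s") go into the medical record and onto the AE CRF. Here too, the new-therapy condition belongs only to the 90-day SAE period.
- **SAP 9.7.1:** an event is treatment-emergent if it starts on or after the first dose and "within 30 days following the last dose of study drug". New therapy plays no part. SAP Section 8 likewise caps certain imputed AE start dates at last dose plus 30 days.

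Two pointers lead sites to 6.2.1. Protocol 4.1.3 names it as the description of the AE reporting period, and Appendix 5 footnote z makes only related SAEs mandatory once that period is over.

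**The concern.** Characterizing safety is the primary objective, and TEAE frequency and severity are listed first among the SAP's safety endpoints. A TEAE summary assumes that events were sought throughout the window in which they are counted. Under the acalabrutinib rule in 6.2.1, full reporting can stop before that window closes, and it stops when a subject moves on to another treatment.

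A day with no required reporting then looks the same in the tables as a day with no event. Any resulting bias would be toward under-counting, and whether it arises would depend on which section a site follows. A site cannot both use the 6.2.1 cut-off and comply with 4.3 as written.

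**Working it through.** The plan gives no figure to reproduce here, so the check sets the rules side by side and then sizes the gap for one subject under stated assumptions.

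**Step 1. End of full AE reporting or counting**

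| Source | End point | Cut at new therapy? |
|---|---|---|
| Protocol 6.2.1, acalabrutinib | last acalabrutinib dose + 30 days | Yes |
| Protocol 6.2.1, pembrolizumab | last pembrolizumab dose + 30 days | No |
| Protocol 4.3 | last dose + 30 (+7) days | No, explicitly |
| Protocol 6.2.2 | cessation of study drug(s) + 30 days | No |
| SAP 9.7.1 | last dose + 30 days | No |

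Only the acalabrutinib rule in 6.2.1 stands apart.

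**Step 2. Who is exposed.** Count days from the last acalabrutinib dose. Let t be the day new anticancer therapy starts (0 to 30), and g the number of days by which the last pembrolizumab dose preceded the last acalabrutinib dose.

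- The acalabrutinib rule gives full reporting to day t.
- The pembrolizumab rule gives full reporting to day 30 − g.
- The SAP window runs to day 30.

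Days in the SAP window without full reporting = 30 − max(t, 30 − g) = min(30 − t, g).

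The result is zero when g = 0. A gap therefore needs both new therapy within 30 days and a last pembrolizumab dose earlier than the last acalabrutinib dose.

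**Step 3. Numbers.** The documents give no distribution for t or g, so both are assumptions. The value g = 21 is one full interval of the 3-weekly pembrolizumab schedule (Protocol 3.5).

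| Last pembrolizumab relative to last acalabrutinib | t = 7 | t = 14 | t = 21 |
|---|---|---|---|
| Same day (g = 0) | 0 | 0 | 0 |
| 21 days earlier (g = 21) | min(23, 21) = 21 | min(16, 21) = 16 | min(9, 21) = 9 |
| 30 or more days earlier | 23 | 16 | 9 |

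As shares of the 30 days, 23, 16 and 9 are 77%, 53% and 30%. The extreme is 30 of 30 days, at t = 0 with g of at least 30.

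**Step 4. Who has a large g.** Protocol 3.6 limits pembrolizumab to 103 weeks, and Protocol 5.1 says enrollment closed in May 2017. By about mid-2019 nearly everyone still on treatment would be on acalabrutinib alone; the SAP is dated 17 January 2020. Subjects who stopped pembrolizumab early and continued acalabrutinib are in the same position.

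**Step 5. What can be missed.** After the 6.2.1 cut-off, related SAEs and related AEs of concern are still reported. What can be lost is unrelated AEs, and non-serious AEs not judged of concern.

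**The case against.** The strongest reply is that the protocol already requires full collection. Section 4.3 and 6.2.2 both say so, Appendix 5 marks AEs at the safety follow-up visit, and its footnote c makes that visit required. Sites following these would lose nothing. This stands as a limit: the gap arises only where a site applies 6.2.1. It does not remove the conflict, because 4.1.3 sends sites to 6.2.1 for the reporting period.

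A reader might infer that TEAE incidence is understated in this trial. The documents do not support that. Lost window days are not lost incidence, and the number of affected subjects is not given. All 161 subjects already had at least one AE at the September 2017 cutoff (Protocol 1.4.2.1), so that overall percentage cannot rise. Only particular terms, grades or disease groups could change.

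A reader might also set a 16-day loss against the median exposure of 3.4 months: 16 / (about 103 + 30) = about 12%. That median covers all subjects, many of whom may have stopped both drugs together, and it does not describe the acalabrutinib-alone group. For a subject treated to Week 103 the window is at least 103 × 7 + 30 = 751 days, and 16/751 is about 2%. Either figure describes one affected subject, not the trial.

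It is also fair that events after new therapy are confounded by that therapy, so stopping at new therapy is a defensible choice. The sections and the SAP would still have to make the same choice.

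Finally, the SAP was written for Amendment 6, the protocol's change summary says AE-reporting language in 4.3 and 6.2.1 was updated, and the protocol's amendment number could not be confirmed from the text reviewed. The mismatch with the SAP may partly reflect versions. The conflict inside the protocol does not depend on that.

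**Conclusion.** The inconsistency is real and should be corrected. The acalabrutinib rule in 6.2.1 contradicts 4.3 and 6.2.2, and it can end full AE reporting before the SAP stops counting TEAEs.

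Its reach is narrow: subjects who start new therapy within 30 days of the last acalabrutinib dose and whose last pembrolizumab dose was earlier, mainly those on acalabrutinib alone, at sites that apply 6.2.1. For such a subject, up to 23, 16 or 9 of the 30 days lack full reporting if new therapy starts on day 7, 14 or 21. Those start days are assumptions. The trial-level effect on TEAE incidence cannot be computed from the documents, and no claim about its size should be made.

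**What to change.** 1. **Protocol 6.2.1:** delete the alternative that ends acalabrutinib AE reporting at the start of new anticancer therapy, together with its whichever-is-first qualifier. The section then agrees with 4.3, 6.2.2 and the SAP window.
2. **SAP 9.7.1:** flag TEAEs that start after new anticancer therapy. Events already missed cannot be recovered by an amendment, and the flag shows which part of the window may be incomplete.
3. **If the sponsor prefers to keep the clause:** change 4.3 and 6.2.2 to match it, and end the SAP's TEAE window at new therapy.

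The cost is one protocol clause and a sentence in the SAP, plus a few more days of AE entry at a visit already scheduled. No new data item is needed: the start of next treatment is already required for time-to-next treatment, and SAP Section 8 already covers partial dates for it. The drawback is that some added events will be confounded by the new therapy; the flag lets them be shown separately.

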# 6.2.2 Assessment of Adverse Events

Investigators will assess the occurrence of AEs and SAEs at all subject evaluation timepoints during the study. All AEs and SAEs whether volunteered by the subject, discovered by study personnel during questioning, or detected through physical examination, or other means, that occur to any subject from the time of first dose through 30 days following the cessation of study drug(s), and all SAEs that occur to any subject receiving pembrolizumab from the time of first dose through 90 days following cessation of pembrolizumab, or 30 days following cessation of pembrolizumab if the subject initiates new anticancer therapy (whichever is earlier) will be recorded in the subject's medical record and on the AE CRF.

Disease progression itself is not considered an AE unless it is considered to be drug-related by the investigator; however, signs and symptoms of disease progression may be recorded as AEs or SAEs.

Each recorded AE or SAE will be described by its diagnostic term, duration (e.g., start and end dates), severity, regulatory seriousness criteria, if applicable, suspected relationship to the study drugs (see following guidance), and any actions taken. The causality of AEs to the study drugs will be assessed by means of the question: 'Is there a reasonable possibility that the event may have been caused by the study drugs?' per FDA guidance on safety reporting requirements (FDA Drug Safety Communication 2012).

See Appendix 3 for more detail on assessing causality.

# 6.2.3 Second Primary Malignancies

AEs for malignant tumors reported during a study should generally be assessed as SAEs. If no other seriousness criteria apply, the "Important Medical Event" criterion should be used. In certain situations, however, medical judgment on an individual event basis should be applied to clarify that the malignant tumor event should be assessed and reported as a nonserious AE. For example, if the tumor is included as medical history and progression occurs during the study but the progression does not change treatment and/or prognosis of the malignant tumor, the AE may not fulfil the attributes for being assessed as serious, although reporting of the progression of the malignant tumor as an AE is valid and should occur. Also, some types of malignant tumors, which do not spread remotely after a routine treatment that does not require hospitalization, may be assessed as nonserious; examples in adults include Stage 1 basal cell carcinoma and Stage 1A1 cervical cancer removed via cone biopsy.

The above instruction applies only when the malignant tumor event in question is a new malignant tumor (i.e., it is not the tumor for which entry into the study is a criterion and that is being treated by the investigational product (IP) under study and is not the development of new or progression of existing metastasis to the tumor under study). Malignant tumors that—as part of normal, if rare, progression—undergo transformation (e.g., Richter's transformation of B-cell chronic lymphocytic leukemia into diffuse large B-cell lymphoma) should not be considered a new malignant tumor.

# 6.2.4 Pregnancy

The investigator should report all pregnancies and pregnancies in the partners of subjects within 24 hours using the Pregnancy Report Form. This form should be faxed or emailed to Acerta Pharma Drug Safety. Any pregnancy-associated SAE must be reported to Acerta Pharma, according to the usual timelines and directions for SAE reporting (see Section 6.2.4).

Any uncomplicated pregnancy that occurs with the subject or with the partner of a treated subject during this study will be reported. All pregnancies and partner pregnancies that are identified during or after this study, wherein the estimated date of conception is determined to have occurred from the time of consent to 2 days after the last dose of acalabrutinib, or within 120 days after the last dose of pembrolizumab or 30 days after the last dose of pembrolizumab if the subject initiates a new anticancer therapy (whichever is earlier of the pembrolizumab dosing situations) will be reported, followed to conclusion, and the outcome reported, as long as the subject or partner is willing to participate in follow-up.

A pregnancy itself is not regarded as an AE unless there is suspicion that the investigational product under study may have interfered with the effectiveness of a contraceptive medication. Likewise, elective abortions without complications are not considered AEs. Any SAEs associated with pregnancy (e.g., congenital abnormalities/birth defects/spontaneous miscarriage or any other serious events) must additionally be reported as such using the SAE form.

Subjects should be instructed to immediately notify the investigator of any pregnancies. Any female subjects receiving study drug who become pregnant must immediately discontinue study drug. The investigator should counsel the subject, discussing any risks of continuing the pregnancy and any possible effects on the fetus.

Upon completion of the pregnancy, additional information on the mother, pregnancy, and baby will be collected and sent to PPD

# 6.2.5 Expedited Reporting Requirements for Serious Adverse Events

All SAEs must be reported within 24 hours of discovery. All initial SAE reports and follow-up information will be reported using the protocol-specific electronic data capture system. If electronic SAE reporting is not available, paper SAE forms must be emailed or faxed to Acerta Pharma Drug Safety (see Table 12), or designee. These must also be completed within 24 hours of the discovery of the SAE. Acerta Pharma may request follow-up and other additional information from the investigator (e.g., hospital admission/discharge notes and laboratory results).

Whenever possible, AEs/SAEs should be reported by diagnosis term, not as a constellation of symptoms.

Death due to disease progression should be recorded on the appropriate form in the electronic data capture system. If the primary cause of death is disease progression, the death due to

disease progression should not be reported as an SAE. If the primary cause of death is something other than disease progression, then the death should be reported as an SAE with the primary cause of death as the event term, as death is typically the outcome of the event, not the event itself. The primary cause of death on the autopsy report should be the term reported. Autopsy and postmortem reports must be forwarded to Acerta Pharma Drug Safety, or designee, as outlined above.

If study drug is discontinued because of an SAE, this information must be included in the SAE report.

An SAE may qualify for mandatory expedited reporting to regulatory authorities if the SAE is attributable to the investigational product (or if a causality assessment is not provided for the SAE, in which case the default of 'related' must be used for expedited reporting purposes) and the SAE is not listed in the current acalabrutinib IB (i.e., an unexpected event). In this case, Acerta Pharma Drug Safety/Designee will forward a formal notification describing the suspected unexpected serious adverse reaction (SUSAR) to all investigators. Each investigator must then notify his or her IRB/IEC of the SUSAR.

# 6.2.6 Reporting Events of Clinical Interest

Selected non-serious and serious AEs are also known as ECIs and must be reported to the sponsor.

For the time period beginning when the consent form is signed until treatment allocation/randomization, any ECI, or follow up to an ECI, that occurs to any subject must be reported within 24 hours to the sponsor if it causes the subject to be excluded from the trial, or is the result of a protocol-specified intervention, including but not limited to washout or discontinuation of usual therapy, diet, placebo treatment or a procedure.

For the time period beginning at treatment allocation/randomization through 30 days following cessation of treatment, any ECI, or follow up to an ECI, whether or not related to study drug

must be reported within 24 hours to the sponsor either by electronic media or paper as described in Section 6.2.5.

Events of Clinical Interest for this trial include:

- 1) An overdose of study drug (overdose is defined in Section 3.10.10) that is not associated with clinical symptoms or abnormal laboratory results.
- An elevated AST or ALT lab value that is ≥3 times the ULN and an elevated total bilirubin value that is ≥2 times ULN and, at the same time, an alkaline phosphatase value that is
   <2 times the ULN, as determined by way of protocol-specified laboratory testing or unscheduled laboratory testing.a
- 3) Ventricular arrhythmias (e.g., ventricular extrasystoles, ventricular tachycardia, ventricular arrhythmia, ventricular fibrillation).
- a These criteria are based upon available regulatory guidance documents. The purpose of the criteria is to specify a threshold of abnormal hepatic tests that may require an additional evaluation for an underlying etiology. The guidance for assessment and follow-up of these criteria for potential drug-induced liver injury can be found in Appendix 7.

